9. MANAGEMENT AND REPORTING OF ADVERSE EVENTS/ADVERSE REACTIONS

Data is anonymized and extracted, analyzed, validated and reported in aggregate.

There is no potential that any employee of BI or agent working on behalf of BI will access individual patient data in which the patient may be identified during data compilation, data reporting or data analysis.

Based on current guidelines from the International Society for Pharmacoepidemiology [R11-4318] and the EMA [R13-1970], non-interventional studies such as the one described in this protocol, conducted using health care records, do not require expedited reporting of suspected adverse events/reactions. Specifically, as stated in section VI.C.1.2.1 of Guideline on Good Pharmacovigilance Practices (GVP), Module VI – Management and Reporting of Adverse Reactions to Medicinal Products, for non-interventional study designs, which are based on use of secondary data, reporting of adverse reactions is not required.

10. PLANS FOR DISSEMINATION AND COMMUNICATION OF **STUDY RESULTS**

We plan to publish the study in a peer-reviewed medical journal.

Authorship and publication will follow the corresponding BI SOP 001-MCS-00-002 and guidelines of good scientific practice.

Proprietary confidential information © 2019 Boehringer Ingelheim International GmbH or one or more of its affiliated companies

12. FUNDING

There are no additional sources of funding.

13. ANNEX

ANNEX 1: LIST OF STAND-ALONE DOCUMENTS

Documents listed in Annex 1 can be maintained separately from the study protocol. They should be clearly identifiable and provided on request. Write "None" if there is no document or list documents in a table as indicated below.

Number	Document reference number	Date	Title
1	None	None	None

ANNEX 2: ENCEPP CHECKLIST FOR STUDY PROTOCOLS

ENCePP Checklist for Study Protocols (Revision 2, amended)

Adopted by the ENCePP Steering Group on 14/01/2013

Study title:

Safety and effectiveness of maintenance treatment with combination of Tiotropium and Olodaterol in comparison to maintenance treatment with a combination of Inhaled Corticosteroids, Long-acting $\beta 2$ agonists and long-acting muscarinic antagonists in COPD patients

Study reference number:

205.526

Section 1: Milestones	Yes	No	N/A	Page
				Number(s)
 1.1 Does the protocol specify timelines for 1.1.1 Start of data collection1 1.1.2 End of data collection2 1.1.3 Study progress report(s) 1.1.4 Interim progress report(s) 1.1.5 Registration in the EU PAS register 1.1.6 Final report of study results. 				15 15 15 15 15
	\bowtie			

Comments:

Section 2: Research question	Yes	No	N/A	Page Number(s)
2.1Does the formulation of the research question and				
objectives clearly explain:				
2.1.1 Why the study is conducted? (e.g. to address an important public health concern, a risk identified in the risk	\boxtimes			17
management plan, an emerging safety issue)				
2.1.2 The objective(s) of the study?	\square			17
2.1.3 The target population? (i.e. population or				
subgroup to whom the study results are intended to be				1/
generalized)				
2.1.4 Which formal hypothesis(-es) is (are) to be				
tested?	_			
2.1.5 If applicable, that there is no a priori hypothesis?			\bowtie	
Comments:				

¹ Date from which information on the first study is first recorded in the study dataset or, in the case of secondary use of data, the date from which data extraction starts. ² Date from which the analytical dataset is completely available.

Proprietary confidential information © 2019 Boehringer Ingelheim International GmbH or one or more of its affiliated companies

Section 3: Study design	Yes	No	N/A	Page Number(s)
3.1 Is the study design described? (e.g. cohort, case- control, randomized controlled trial, new or alternative design)	\boxtimes			18
3.2 Does the protocol specify the primary and secondary (if applicable) endpoint(s) to be investigated?	\boxtimes			18
3.3 Does the protocol describe the measure(s) of effect? (e.g. relative risk, odds ratio, deaths per 1000 person-years, absolute risk, excess risk, incidence rate ratio, hazard ratio, number needed to harm (NNH) per year)				25-27
Comments:				

Section 4: Source and study populations	Yes	No	N/A	Page Number(s)
4.11s the source population described?	\square			18, 22
 4.2Is the planned study population defined in terms of: 4.2.1 Study time period? 4.2.2 Age and sex? 4.2.3 Country of origin? 4.2.4 Disease/indication? 4.2.5 Co-morbidity? 4.2.6 Seasonality? 	\mathbb{X} \mathbb{X} \mathbb{X} \mathbb{X}			18 18 18 18, 22 18, 20-21 20
4.3 Does the protocol define how the study population will be sampled from the source population? (e.g. event or inclusion/exclusion criteria)				18

Comments:

Section 5: Exposure definition and measurement	Yes	No	N/A	Page Number(s)
5.1 Does the protocol describe how exposure is defined and measured? (e.g. operational details for defining and categorizing exposure)	\boxtimes			19
5.2 Does the protocol discuss the validity of exposure measurement? (e.g. precision, accuracy, prospective ascertainment, exposure information recorded before	\boxtimes			19, 22

Section 5: Exposure definition and measurement	Yes	No	N/A	Page Number(s)
the outcome occurred, use of validation sub-study)				
5.3 Is exposure classified according to time windows? (e.g. current user, former user, non-use)	\boxtimes			19
5.4 Is exposure classified based on biological mechanism of action and taking into account the pharmacokinetics and pharmacodynamics of the drug?				
5.5 Does the protocol specify whether a dose- dependent or duration-dependent response is measured?				
Comments:				

Section 6: Endpoint definition and measurement	Yes	No	N/A	Page Number(s)
6.1 Does the protocol describe how the endpoints are defined and measured?	\boxtimes			19-20
6.2 Does the protocol discuss the validity of endpoint measurement? (e.g. precision, accuracy, sensitivity, specificity, positive predictive value, prospective or retrospective ascertainment, use of validation sub- study)				19-20, 22

Section 7: Confounders and effect modifiers	Yes	No	N/A	Page Number(s)
7.1 Does the protocol address known confounders?(e.g. collection of data on known confounders, methods of controlling for known confounders)	\boxtimes			20-21
7.2 Does the protocol address known effect modifiers? (e.g. collection of data on known effect modifiers, anticipated direction of effect)				22
Comments:	•	•	•	

c30699487-01

Section 8: Data sources	Yes	No	N/A	Page Number(s)
8.1 Does the protocol describe the data source(s) used in the study for the ascertainment of:				
8.1.1 Exposure? (e.g. pharmacy dispensing, general practice prescribing claims data self-report face-				22
to-face interview, etc.)				22
8.1.2 Endpoints? (e.g. clinical records, laboratory markers or values, claims data, self-report, patient interview including scales and questionnaires, vital statistics, etc.)				22
8.1.3 Covariates?				
8.2 Does the protocol describe the information available from the data source(s) on:				
8.2.1 Exposure? (e.g. date of dispensing, drug quantity, dose, number of days of supply	\boxtimes			22
prescription, daily dosage, prescriber)	\square			
8.2.2 Endpoints? (e.g. date of occurrence, multiple event, severity measures related to event)	\boxtimes			22
8.2.3 Covariates? (e.g. age, sex, clinical and drug use history, co-morbidity, co-medications, life style, etc.)				22
8.3 Is a coding system described for:				
8.3.1 Diseases? (e.g. International Classification of Diseases (ICD)-10)				22
8.3.2 Endpoints? (e.g. Medical Dictionary for	\square			22
events)	\bowtie			22
8.3.3 Exposure? (e.g. WHO Drug Dictionary, Anatomical Therapeutic Chemical (ATC)Classification System)				
8.4 Is the linkage method between data sources described? (e.g. based on a unique identifier or other)				
Comments:				

Section 9: Study size and power	Yes	No	N/A	Page Number(s)
9.1 Is sample size and/or statistical power calculated?	\boxtimes			22-23
Comments:				

Section 10: Analysis plan	Yes	No	N/A	Page Number(s)
10.1 Does the plan include measurement of excess risks?				25-27
10.2 Is the choice of statistical techniques described?	\boxtimes			25-27
10.3 Are descriptive analyses included?	\boxtimes			25
10.4 Are stratified analyses included?	\boxtimes			25-27
10.5 Does the plan describe methods for adjusting for confounding?	\boxtimes			25-27
10.6 Does the plan describe methods addressing effect modification?	\boxtimes			25-27
Comments:				

Secti	on 11. Data management and quality control	Vos	No	N/A	Рада
5000	on 11. Data management and quanty control	105	110	1 1 /A	Number(s)
11.1	Is information provided on the management of missing data?				22
11.2	Does the protocol provide information on data storage? (e.g. software and IT environment, database maintenance and anti-fraud protection, archiving)				24
11.3	Are methods of quality assurance described?	\square			24
11.4	Does the protocol describe possible quality issues related to the data source(s)?				24
11.5	Is there a system in place for independent review of study results?				27
Comn	nents:				

Section 12: Limitations	Yes	No	N/A	Page Number(s)
 12.1 Does the protocol discuss: 12.1.1 Selection biases? 12.1.2 Information biases? (e.g. anticipated direction and magnitude of such biases, validation sub-study, use of validation and external data, analytical methods) 				22, 28
12.2 Does the protocol discuss study feasibility? (e.g. sample size, anticipated exposure, duration of				22-23

Proprietary confidential information © 2019 Boehringer Ingelheim International GmbH or one or more of its affiliated companies

Section 12: Limitations	Yes	No	N/A	Page Number(s)
follow-up in a cohort study, patient recruitment)				
12.3 Does the protocol address other limitations?	\square			22, 28
Comments:				

Section 13: Ethical issues	Yes	No	N/A	Page
				Number(s)
13.1 Have requirements of Ethics Committee/Institutional Review Board approval been described?	\boxtimes			28-29
13.2 Has any outcome of an ethical review procedure been addressed?			\square	
13.3 Have data protection requirements been described?				24
Comments:				

Section 14: Amendments and deviations	Yes	No	N/A	Page Number(s)
14.1 Does the protocol include a section to document future amendments and deviations?	\boxtimes			14

Comments:

Section 15: Plans for communication of study results	Yes	No	N/A	Page Number(s)
15.1 Are plans described for communicating study results (e.g. to regulatory authorities)?				
15.2 Are plans described for disseminating study results externally, including publication?	\boxtimes			29
Comments:				

Name of the main author of the protocol: Date: 16 August 2019

Signature: _____

Proprietary confidential information © 2019 Boehringer Ingelheim International GmbH or one or more of its affiliated companies

ANNEX 3: ADDITIONAL INFORMATION

Additional annexes may be included if necessary.

ANNEX 3.1: DEFINITION OF STUDY EXPOSURES

Medication	HCPCS	GPI
LABA (single)		
Indacaterol		44201042X
Salmeterol		4420105810X
Formoterol	J7605, J7606, J7640, O4099	44201027X 44201012102520
Olodaterol		44201052X
LAMA (single)		
Tiotropium	1	44100080X
Aclidinium		44100007X
Glycopyrronium	J7642, J7643	44100020X
Umeclidinium		44100090X
Revefenacin		44100075002020
ICS (single)		4440X
		4220X
Fluticasone	J7641	44400033X
Budesonide	J7626, J7627, J7633, J7634	44400015X
Beclomethasone	J7622	42200010x
		44400010x
Mometasone		42200045101820
		44400036X
Flunisolide	J7641	44400030X
Ciclesonide		4440001700x
Dexamethasone		4440002010x
Triamcinolone	J7683, J7684	4440004020x
LABA/LAMA		
Formoterol/glycopyrroni um		44209902543220

c30699487-01

Proprietary confidential information © 2019 Boehringer Ingelheim International GmbH or one or more of its affiliated companies

Medication	HCPCS	GPI
Indacaterol/glycopyrroni um		44209902600110
Vilanterol/umeclidinium		4420990295X
Olodaterol/tiotropium		4420990292X
LABA-LAMA-ICS		
Fluticasone furoate/umeclidinium/vil anterol		44209903408020

ANNEX 3.2: DEFINITIONS OF STUDY OUTCOMES

Condition	ICD9	ICD10	ICD9 proc	ICD10 proc	HCPCS	CPT
COPD	491	J41	1	1		
	491	J41.0				
	491.1	J41.1				
	491.2	J41.8				
	491.21	J42				
	491.22	J43				
	491.8	J43.0				
	491.9	J43.1				
	492	J43.2				
	492	J43.8				
	492.8	J43.9				
	496	J44				
		J44.0				
		J44.1				
		J44.9				
Pneumonia	480	J10.00				
	480.1	J10.01				
	480.2	J10.08				
	480.3	J11.00				

Boehringer Ingelheim		
Protocol for non-interventional	studies based on	existing data
BI Study Number 1237-0094		

	480.8	J11.08
	480.9	J12.0
	481	J12.1
	482	J12.2
	482.1	J12.3
	482.2	J12.81
	482.3	J12.89
	482.31	J12.9
	482.32	J13
	482.39	J14
·	482.4	J15.0
·	482.41	J15.3
	482.42	J15.4
	482.49	J15.5
	482.81	J15.6
	482.82	J15.7
	482.83	J15.8
·	482.84	J15.9
	482.89	J16.0
·	482.9	J16.8
	483	J17
·	483.1	J18.0
	483.8	J18.1
	484.1	J18.2
	484.3	J18.8
	484.5	J18.9
	484.6	J69.0
	484.7	J85.1
	484.8	J95.4
·	485	J95.89
	486	*
	997.31	
	·	1

c30699487-01

Proprietary confidential information © 2019 Boehringer Ingelheim International GmbH or one or more of its affiliated companies

|--|

Medication	HCPCS	GPI
Prednisolone	J2650, J7510, J7512	22100040X 22109902201810
		22100045X

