7.4 VARIABLES

7.4.1 **Exposures**

The exposure measures are based on pharmacy dispensings of the study medications, namely Tio+Olo and LABA/LAMA/ICS combination therapy. As described in the data analysis section, the as-treated analysis, which is the main analysis, will consider continuing exposure of the initial treatment of Tio+Olo or LABA/LAMA/ICS within the treated groups defined by the days supply recorded at the time of pharmacy dispensing, allowing for a gap between dispensings of up to 15 days. This gap is allowed in consideration of plausible delays in obtaining medication refills and continued use beyond the days supplied where medication has been missed due to imperfect adherence, and will be varied in sensitivity analyses (see Section 7.9.2). Codes used to identify study medications are included in Annex 3.1.

The treatment segment ends at the earliest of the following events:

- 1. Fifteen days after the end of the observed days supply for the medication received on the index date without a subsequent dispensing of COPD medication (i.e., discontinuation)
- 2. Initiation of triple therapy (i.e., addition of ICS to Tio+Olo or a LAMA to LABA/ICS (i.e., treatment escalation, applies to Tio+Olo only)
- 3. Any other change in use of study medication by active ingredient, inclusive of a change to a different combination therapy, change from a fixed form to a free form combination therapy, or a change from combination therapy to monotherapy (i.e., switch)

Changes in dose for medications started on the index date will not impact the end of the treatment segment. Codes used to identify study medications are included in Annex 3.1.

7.4.2 **Outcome(s)**

7.4.2.1 **Primary outcome(S)**

The primary outcome event for effectiveness is the first COPD exacerbation to occur after cohort entry. The event is defined as follows:

- Severe exacerbation: •
 - Hospitalization with a principal discharge diagnosis of COPD.
 - Moderate exacerbation:
 - An ED visit with a discharge diagnosis of COPD and/or
 - Dispensing of an antibiotic and an oral corticosteroid on the same day

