Time to the first COPD exacerbation will be measured from cohort entry until the occurrence of a hospitalization for COPD (severe exacerbation) or ED visit for COPD with the prescription of an antibiotic and/or an oral corticosteroid on the same day (moderate exacerbation). Severe and moderate exacerbations will be considered as a composite for main analyses. Sensitivity analyses will stratify by exacerbation severity.

Although there is precedent for defining moderate exacerbation based on use of antibiotics for a respiratory infection without requiring concomitant oral corticosteroids, we have chosen

a more restrictive definition of exacerbation. Because diagnoses listed on outpatient claims often correspond to a patient's past medical history in addition to acute problems, we expect limited ability to capture the indication for which antibiotics are prescribed. As such, including antibiotics alone as a case definition for exacerbation would introduce potentially substantial misclassification of outcome where antibiotics were truly given for non-respiratory infections. Given that our analyses will yield estimates on a ratio measure, non-differentially reduced sensitivity is a less important threat to validity than reduction of outcome specificity, which produces an expectation of bias towards the null hypothesis. In order to test our assumptions that the sensitivity of our outcome definition is not differential between the Tio+Olo and LABA/ICS groups, we would produce counts of patients with antibiotics alone during follow-up, and determine whether the proportion of potential exacerbations that we excluded through this design decision is comparable across groups.

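### Section 7.4.2.1 counts any oral corticosteroid, but Annex 3.2 codes the class with a single prednisolone row, so some dispensing-based exacerbations would not count

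*Combined protocol and SAP*

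**What the plan says.** Section 7.4.2.1 defines the primary outcome, the first COPD exacerbation, in two ways.

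- **List.** A severe event is "Hospitalization with a principal discharge diagnosis of COPD". A moderate event is "An ED visit with a discharge diagnosis of COPD and/or" "Dispensing of an antibiotic and an oral corticosteroid on the same day".
- **Narrative just below it.** A moderate event is an "ED visit for COPD with the prescription of an antibiotic and/or an oral corticosteroid on the same day".

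Both refer to oral corticosteroids as a class. The codes are in Annex 3.2. Its medication table has one named row, Prednisolone, with HCPCS codes "J2650, J7510, J7512", GPI codes "22100040X 22109902201810", and a further GPI code, 22100045X, on a line with no drug name. The documents do not say what each code stands for.

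Oral methylprednisolone appears in none of Annexes 3.1 to 3.3. Dexamethasone appears once, under single-agent inhaled corticosteroids in Annex 3.1.

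Section 7.4.2.1 also defends a restrictive definition, on the ground that "non-differentially reduced sensitivity is a less important threat to validity than reduction of outcome specificity". As a check on that assumption it says "we would produce counts of patients with antibiotics alone during follow-up".

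**The concern.** The programmer builds the outcome from the annex. If the annex is narrower than the text, a patient who fills an antibiotic and an unlisted oral corticosteroid on one day meets the written definition but is not counted.

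Three things would be at stake:

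- **Events.** Moderate exacerbations are lost or delayed, both in the composite and in the separate moderate analysis planned in Section 7.9.1.
- **The planned check.** These patients would enter the antibiotics-alone count. That count could then not separate the deliberate exclusion from an omission in the code list.
- **Baseline history.** If history were built from the same fills, missed courses could affect the low-risk and high-risk strata.

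The stated rationale does not cover this. The preference for specificity is argued only for leaving out antibiotics given alone. Nothing in the protocol justifies limiting which oral corticosteroid counts.

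**Working it through.** **1. Does the row look like shorthand for the class?** Compare the other drug lists. Annex 3.1 names eight inhaled corticosteroids one by one and adds the class-level codes 4440X and 4220X. Annex 3.3 names 37 antibiotics. The oral corticosteroid list has one drug name and no code labelled as covering the class.

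**2. Which events depend on the list?**

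| Route | Under the list | Under the narrative |
|---|---|---|
| COPD hospitalization | No steroid code needed | No steroid code needed |
| ED visit for COPD | No steroid code needed | Lost only if the sole drug is an unlisted corticosteroid |
| Same-day dispensing without ED visit | Lost if the corticosteroid is unlisted | Not an event at all |

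The two definitions conflict, and the size of the problem depends on which one is run.

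**3. The plan's own power figure.** Section 7.7 cites over 90% power for a hazard ratio of 0.85 with 2,000 patients per cohort. By Schoenfeld's formula, events = (z for alpha + z for power)² / [p(1−p)(ln HR)²]. With two-sided alpha 0.05 (assumed), 90% power and p = 0.5, this is (1.960 + 1.282)² / [0.25 × (ln 0.85)²] = 1,592 events. That is 1,592/4,000 = 39.8% of patients. Section 7.7 gives no event risk, so the figure is plausible but can be neither reproduced nor refuted.

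**4. Precision with the preliminary cohorts.** Section 7.7 gives 5,469 and 42,227 patients, in total 47,696, so p = 5,469/47,696 = 0.115. The same formula requires 3,919 events for 90% power, which is 8.2% of patients. Power with D events is Φ(|ln HR| × √[D p(1−p)] − 1.96), where D = 47,696 × event risk × (1 − share missed). Event risk and share missed are assumptions. Weighting is ignored.

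| Event risk | 0% missed | 10% | 20% | 30% |
|---|---|---|---|---|
| 5% | 71.5% | 67.0% | 61.9% | 56.2% |
| 10% | 94.7% | 92.4% | 89.2% | 84.9% |
| 20% | 99.9% | 99.8% | 99.5% | 98.8% |

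The standard error of the log hazard ratio rises by 1/√(1 − share missed): 1.05, 1.12 and 1.20 for 10%, 20% and 30%.

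**5. Bias.** With perfect specificity and uncommon events, observed ratio ≈ true ratio × Se1/Se0, where Se1 and Se0 are the sensitivities in the two arms. If they are equal (0.9, 0.8 or 0.7 in both), 0.85 stays 0.85. If they are 0.85 and 0.80, it becomes 0.85 × 0.85/0.80 = 0.90. Reversed, it becomes 0.85 × 0.80/0.85 = 0.80.

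**The case against.** **The table may be incomplete in the copy read here.** A broken fragment precedes it, one code has no drug name, and Annex 3.2 shows no antibiotic rows although the outcome needs them (they are in Annex 3.3). The codes are also not decoded, so the row label does not prove what they exclude. This stands as a reason to check the original table first. It does not remove the mismatch in the text as it reads.

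**The protocol accepts lower sensitivity, and the planned count would show a difference between arms.** This stands in part. Equal loss leaves the ratio unchanged, and a differential loss would appear in the antibiotics-alone count. It would appear only indirectly, mixed with the events excluded on purpose.

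Several stronger readings are tempting, and the documents do not support them:

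- *All exacerbations treated with another corticosteroid are missed.* Hospitalizations count regardless, and so do COPD ED visits under the list.
- *A definite fraction of first events is lost.* That fraction would be the unlisted share, times the share found only by dispensing, times one minus the share with a later detected event. The documents give none of the three. A patient whose course is missed also stays at risk, so a later hospitalization, ED visit or listed course still counts.
- *Patients are moved into the low-risk stratum.* Section 7.4.3 describes moderate baseline events by ED visits or by inhaled corticosteroids and antibiotics, so it is not established that history uses the oral list.
- *One of the listed codes is not an oral product.* The documents do not define the codes, so this can only be a request to verify.

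**Conclusion.** The concern holds as a mismatch between the primary-outcome text and its code list. As written, an antibiotic with an unlisted oral corticosteroid meets the definition in the list of Section 7.4.2.1 but would not be counted. The loss is confined to events found only through dispensing if the list is followed, and to ED visits whose sole drug is an unlisted corticosteroid if the narrative is followed.

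The consequence is reduced sensitivity and precision of unknown, possibly modest, size. In the overall cohort it hardly matters at an assumed 20% event risk (power at least 98.8% with 30% of events missed). It is visible at 10% (94.7% down to 84.9%) and clear at 5% (71.5% down to 56.2%). The eosinophil strata, which Section 7.7 already calls more limited, have less to spare. Bias follows only if the choice of agent differs between arms, and nothing in the documents shows that it does.

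These figures rest on two-sided alpha 0.05, a hazard ratio of 0.85, the preliminary counts, and assumed event risks and missed shares. The point is worth correcting because the remedy is cheap and uses existing claims.

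**What to change.** 1. Check the Annex 3.2 medication table in the original for lost rows or headings.
2. If it is as it appears, expand it to all systemic oral corticosteroids, adding at least oral methylprednisolone and oral dexamethasone, with a drug name against every code. If a restriction to certain agents is intended, state and justify it in Section 7.4.2.1.
3. Verify that each listed code is an oral dispensing.
4. Reconcile the list and the narrative in Section 7.4.2.1, so that it is clear whether same-day dispensing without an ED visit counts, and whether an ED visit needs a drug.
5. Use the same list for baseline exacerbation history, and reconcile the reference to inhaled corticosteroids in Section 7.4.3 with it.

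The cost is an annex edit, matching text changes and one re-run. No new data are needed.
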